3.4.2.5. Analysis for Secondary Aim 3: Perinatal Period and Perinatal Depression and Anxiety

We are also **exploring whether the timing of the treatment (antenatal vs. postnatal) influences depressive and anxiety symptoms at 12-months post-randomization.**

This model will also test whether expectant mothers who receive antenatal treatment benefit more in terms of reduced depressive symptoms than mothers who receive postnatal treatment at 12-months post-randomization. A 2-group comparison with at least 200 per group and an assumed mean of EPDS score of 7.93 (SD=4.68)³⁰ will provide 90% power, with an alpha of 0.05, to detect a mean change of 1.5 points. This allows us to detect a drop corresponding to a small effect size of 0.3 (i.e., a drop to mean 6.43 on the EPDS). The two groups' (antenatal vs. postnatal) EPDS scores at 3-months will be compared using a two-sided two-sample t-test. An exploratory analysis will be carried out on this set of patients to test for a group by treatment interaction at 12 months.

3.4.3. Missing Data and Imputation

Multiple imputation methods will be used to impute missing data and compare model results to the complete case analysis. This process will involve assessing the distribution of the original data. Fully conditional specification (FCS) methods will be carried out using SAS's Proc MI and Proc MIANALYZE. The procedure will create five imputed datasets and the model results averaged across the five iterations³⁹. If needed, we will also align the number of imputations to be on par with the percent missingness (i.e., if 10% is missing, 10 imputations), as per the recommendation from PCORI's methodological consultant^{40, 41}. Linear mixed models will be used to assess repeated measures outcomes. These models use maximum likelihood estimation methods that retain participants who do not have complete data across all time points. Reasons for dropout will be ascertained and we will interview a subset of the participants who dropped out and reasons will be coded accordingly. Sensitivity analyses will be carried out should missing data lead to the use of multiple imputation methods. These analyses will compare the results of the models on the imputed data to the ones with the actual missing data included.

3.4.4. Outliers

All the collected data will be checked for any potential outliers or errors or invalidity after importing to SAS³⁵. Any outliers that are acceptable values will be included in the final analysis, but we will consider a possible sensitivity analysis to examine the impact of the outliers.

3.4.5. Treatment Providers

Competency measures including multiple choice exam and role play scores from the training sessions among both types of treatment providers (SP and NSP) will be compared with participant outcomes to determine if competency scores during training predict participant outcomes. In addition, key variables related to therapy quality will include treatment-specific skills (range mean score of 0-4) and general skills (range mean score of 0-4) as measured by the Q-HAP and a total score (range 0-35) of a 35-item multiple choice exam (range total score of 0-35). Means, SDs and ranges of all competency measures for each individual provider and across providers will be calculated. This will be followed by estimating the relations between competency measures by calculating the Pearson correlation. Finally, multiple regression analyses will be used to estimate whether competency measures can predict patient outcome

scores of EPDS and GAD-7 scores post-treatment. Covariates including baseline EPDS scores, and treatment provider will be utilized to account for potential baseline heterogeneity.

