- **3.5.3.3. Treatment Providers.** Competency measures from the training sessions among both types of treatment providers (specialists and non-specialists) will be compared with participant outcomes to determine if competency scores during training predict participant outcomes. Key variables related to competency will include treatment-specific skills (range mean score of 0-4) and general skills (range mean score of 0-4) as measured by the Q-HAP and a total score (range 0-35) of a 35-item multiple choice exam (range total score of 0-35). All analyses will be conducted using SAS 9.4. Means, SDs and ranges of all competency measures for each individual NSP and across NSPs. This will be followed by estimating the relations between competency measures by calculating the Pearson correlation. Finally, multiple regression analyses will be used to estimate whether competency measures can predict patient outcomes scores of EPDS and GAD-7 scores post-treatment. Covariates including baseline EPDS scores and treatment provider will be utilized to account for potential baseline heterogeneity.
- **3.5.4. Qualitative Analysis.** All qualitative data will be analyzed using NVivoTM, a qualitative data analysis software package. We will use content analysis with data analysis (coding) conducted by multiple independent raters, for whom inter-rater reliability will be calculated using Kappa ( $\kappa$ ) scores. Coding will be conducted in a step-wise fashion to facilitate iterative revision and then finalization of a coding scheme. Specifically, there will be a process of first independently coding and then discussing a minimum of 3 cases per stakeholder group to achieve a kappa ( $\kappa$ ) score of  $\kappa$ =0.75 or higher (defined as substantial to almost perfect agreement). Qualitative data will then be quantified and triangulated across stakeholder groups using our previously established methods.
- **3.5.5 Economic Evaluation Analysis.** Our economic evaluation will examine the cost-effectiveness of non-specialist vs. specialist provider and telemedicine vs. in-person sessions (in line with the clinical analyses) and will follow CADTH guidelines . As such, we will adopt the health system perspective.

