3.4.2.3. Analysis for Secondary Aim 2: Clinical Severity

We are also interested in assessing moderating effects of clinical severity (mild, moderate and severe; see [Appendix 2](#) for cut-off values and severity classification for outcomes) on the comparative effectiveness of the two delivery modes on depressive and anxiety symptoms at 3-, 6- and 12-months post randomization.

This will involve the use of linear mixed models. Using a non-inferiority margin of 10%, 10% dropout, and an alpha of 0.05, we require 44 participants³⁸. Mothers will be taken as a random effect and the models will include a treatment-by-time interaction term. Other potential moderators will be explored such as age, ante or postnatal enrollment, patient preference, white/BIPOC, and trauma symptoms. The same set of analyses as above will be conducted for anxiety symptoms (GAD-7), disability scores, quality of life, and client satisfaction.

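### In the competency regression, training-score effects are not estimable if the provider covariate is the individual; if it is provider type, standard errors are too small whenever patients of one provider are correlated

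*SAP*

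**What the plan says.** SAP 3.4.5 sets out to compare exam and role-play scores from provider training with patient results, "to determine if competency scores during training predict participant outcomes". It first describes the scores: "Means, SDs and ranges of all competency measures for each individual provider and across providers will be calculated". It then correlates the measures with one another, and last models the patients: "Finally, multiple regression analyses will be used to estimate whether competency measures can predict patient outcome" scores on the EPDS and GAD-7 after treatment. The adjustment is given in one sentence: "Covariates including baseline EPDS scores, and treatment provider will be utilized to account for potential baseline heterogeneity". Protocol 3.5.3.3 says the same: "Covariates including baseline EPDS scores and treatment provider will be utilized to account for potential baseline heterogeneity".

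The SAP section also names a second kind of predictor: "In addition, key variables related to therapy quality will include treatment-specific skills" and general skills, both rated with the Q-HAP.

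Neither document says whether the provider covariate is the individual or the type. Neither mentions a provider random effect, cluster-robust standard errors or any other allowance for patients sharing a provider. Where random effects are specified, for example in SAP 3.4.2.3, they are for the patient: "Mothers will be taken as a random effect". The only other grouping considered is site (SAP 1.2 and 3.1).

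**The concern.** The exam and the training role play are completed before a provider treats trial patients (protocol 2.3.2 and 2.4). Every patient of one provider therefore carries the same score, and all information about whether the score predicts outcome lies in differences between providers. The effective sample size is closer to the number of providers than to the number of patients.

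The regression as described does not respect this. Terms for individual providers would absorb all between-provider information and leave nothing for the score. A term for provider type alone would leave the score estimable, but each patient would count as independent evidence about it.

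At stake is the claim that an exam or role-play result predicts patient improvement. In a trial about scaling up treatment through trained non-specialists, such a claim could shape how future providers are selected and trained.

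**Working it through.** The plan states no sample size, power or standard error for this analysis, so there is no figure to reproduce. The check takes each reading of the covariate in turn.

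**Inputs from the documents.** Total N is 1,226 with 10% loss (SAP 1.6.2), so 1,226 × 0.9 = about 1,103 patients analysed. The EPDS SD is 4.68 (SAP 1.6.1).

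**Inputs assumed.** The number of providers K, the caseload m, and the ICC that remains after the model's covariates.

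**Reading A: individual provider as a fixed covariate.** The columns are an intercept, baseline EPDS, K − 1 provider indicators and one training score, which makes K + 2. A score that is constant within provider is an exact linear combination of the intercept and the provider indicators, so the rank is K + 1:
- K = 20: 22 columns, rank 21
- K = 40: 42 columns, rank 41
- K = 80: 82 columns, rank 81

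The score's coefficient has no estimate, whatever the number of patients. If the score is replaced by a rating that varies between patients of the same provider, the matrix has full rank (22 of 22, 42 of 42, 82 of 82). The coefficient then describes a within-provider association.

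**Reading B: provider type as the covariate.** Intercept, baseline EPDS, type and score give 4 columns with rank 4, so the effect is estimable. For a predictor constant within provider and equal caseloads, the true variance exceeds the ordinary-regression variance by the design effect

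DE = 1 + (m − 1) × ICC,

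and the naive standard error should be multiplied by √DE.

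*Illustration with caseload assumed:*
- m = 20, ICC 0.02: DE = 1 + 19 × 0.02 = 1.38. The naive SE is 1/√1.38 = 0.85 of the correct one, 15% too small.
- m = 40, ICC 0.05: DE = 1 + 39 × 0.05 = 2.95. The naive SE is 1/√2.95 = 0.58 of the correct one, 42% too small.

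*Wider range, with m = 1,103/K.* Type I error is simulated at nominal two-sided 0.05, with no true competency effect and 1,500 runs per cell:

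| Providers (m) | ICC | DE | √DE | Type I error |
|---|---|---|---|---|
| 20 (55.1) | 0.01 | 1.54 | 1.24 | 0.11 |
| 20 (55.1) | 0.05 | 3.71 | 1.93 | 0.32 |
| 20 (55.1) | 0.10 | 6.42 | 2.53 | 0.45 |
| 40 (27.6) | 0.01 | 1.27 | 1.13 | 0.07 |
| 40 (27.6) | 0.05 | 2.33 | 1.53 | 0.21 |
| 40 (27.6) | 0.10 | 3.66 | 1.91 | 0.30 |
| 80 (13.8) | 0.01 | 1.13 | 1.06 | 0.07 |
| 80 (13.8) | 0.05 | 1.64 | 1.28 | 0.13 |
| 80 (13.8) | 0.10 | 2.28 | 1.51 | 0.18 |

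At ICC 0, DE is 1 and simulated error was 0.04 to 0.05 for all three values of K.

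**The case against.** The best counter-argument is that the section is under-specified rather than wrong. Its list of covariates is not exhaustive. Provider could be meant as a random or clustering term, which would cure both problems, or the regression could be run on one summary per provider. Neither can be excluded, but neither is what the text describes: it names covariates in a multiple regression of patient scores, adjusted for patients' baseline EPDS. An analyst following the text would not arrive at either.

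Provider type is also arguably the more natural reading. The section opens by naming the two types, and SAP Appendix 1 records each provider's designation as NSP or SP. That stands, and it makes the aliasing branch the less likely one. Aliasing would also reveal itself, because the software would return no estimate.

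A reader might infer that no competency effect can be estimated under the individual-provider reading. The documents do not support that. Therapy-quality ratings are made repeatedly, on individual recorded sessions and at supervision (protocol 4.4, SAP Appendix 1). If linked to patients they can vary within provider and would not be aliased. Q-HAP ratings made once, on the standardised patient during training (protocol 2.3.2), remain fixed per provider and would be.

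Finally, competency prediction is not among the listed aims (protocol 1.4, SAP 1.1) and has no stated hypothesis or power. That limits the importance of the point but does not answer it.

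**Conclusion.** The point holds for scores that are fixed per provider, that is, the training exam and role play. On neither natural reading does the written model give reliable inference: the effect is aliased under one, and tested with patient-level standard errors under the other.

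The second branch is conditional. It needs a residual provider ICC above zero after adjustment for baseline EPDS, provider type and competency, and that could be lower than a raw ICC. A reader might conclude that false-positive predictors are certain, or that standard errors are known to be 15% to 42% too small. The documents support neither. That range follows only from the assumed caseloads and ICCs; the wider, equally assumed grid gives correct standard errors 1.06 to 2.53 times the naive ones. Both sets of figures assume equal caseloads.

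This is a minor point with a nearly free remedy. It does not touch either primary non-inferiority comparison.

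**What to change.** Amend SAP 3.4.5, and align protocol 3.5.3.3, to say that:

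- The fixed covariate is provider type (NSP or SP).
- The model is a linear mixed model for the post-treatment score (EPDS, and separately GAD-7), with a random intercept for the individual provider, fixed effects for type, baseline score and site, and competency as a provider-level predictor. The plan's post-treatment time point is kept.
- Tests and intervals for competency use a small-sample degrees-of-freedom correction such as Kenward-Roger.
- Correlated competency measures are entered singly if providers are few. For example, with an assumed 20 providers and the five sites in SAP 3.1, an intercept, type, four site terms and one score use 7 provider-level terms and leave 13 degrees of freedom. Four competency measures entered together would leave 10.
- Therapy-quality ratings that vary within provider are handled separately from the training scores, with a statement of how they are linked to patients.
- The number of providers, and of patients per provider, is reported next to the result.

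The cost is SAP wording; the data are already collected. The downside is wider intervals for an exploratory analysis, and these reflect the information actually available.

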3.4.6. Qualitative Data

Qualitative interviews with participants, significant others, providers, clinical leads, and stakeholders will be conducted to address the following secondary aim 4: **To conduct a process evaluation, i.e., identify the underlying processes related to delivery and scalability of a brief psychological treatment for perinatal depressive and anxiety symptoms from a multi-stakeholder perspective including relevant barriers and facilitators.**

All qualitative data will be analyzed using NVivo™, a qualitative data analysis software package. We will use content analysis with data analysis (coding) conducted by multiple independent raters, for whom inter-rater reliability will be calculated using Kappa (κ) scores. A coding index will be developed and finalized, and the data will be coded in a stepwise fashion to facilitate iterative revision. Specifically, there will be a process of first independently coding and then discussing a minimum of 3 cases per stakeholder group to achieve a kappa (κ) score of $\kappa=0.75$ or higher (defined as substantial to almost perfect agreement). The qualitative data will then be quantified and triangulated across stakeholder groups using our previously established methods.

[figure not shown]
3.4.7. Scalability: An examination of what works (and did not work) for whom

Methods. Once follow-up data (6- and 12-months) have been collected in the SUMMIT Trial, we will attempt to answer the question of ‘what works for whom’ in order to ultimately identify the optimal intervention strategy for each mother (with the ultimate goal of truly **personalized, patient-centered care**)⁴². To do this, we will develop clinical prediction models (CPMs) using validated machine learning approaches⁴³⁻⁴⁵. Although the clinical utility of precision treatment rules (PTRs) informed by CPMs was recently demonstrated in a prospective randomized controlled trial⁴⁶, the approach has never been tested to identify optimal delivery strategy options for perinatal populations with depressive and anxiety symptoms.

Analysis. Developing PTRs for treatment selection will involve the generation of statistical models that capture both prognostic and prescriptive information to predict expected treatment response in two or more conditions. We will use SuperLearner, an ensemble machine learning method^{47, 48} that assigns weights to a set of selected algorithms to develop a consolidated predictive algorithm which optimizes cross-validated *MSE*. Model validation will be performed using bootstrapping, which is the recommended procedure for assessing honest model performance⁴⁹. Recent approaches^{50, 51} will be used to evaluate the benefit that would be expected if the final algorithm were to be used to guide treatment selection.

3.4.8. Mediation: An examination of the conceptual causal model behind the workings of BA

Figure 3. Conceptual causal model behind the workings of BA

within a causal pathway. Because the current study proposes a non-inferiority trial where the same treatment (BA) will be used in all four arms, we anticipate similar pathways in each arm, irrespective of who or how the treatment will be delivered.

This conceptual model involving treatment and patient variables and clinical outcomes has been used in the psychological treatment literature for depression and anxiety, as well as other disorders⁵². In short, this temporal model proposes that active treatment ingredients (processes that occur during intervention delivery) influence patient behaviors (in this case, improvements in patient-reported activation, perceived support and therapeutic alliance), which in turn influence clinical outcomes (reduced depressive and anxiety symptoms). The proposed model also extends the existing psychological treatment literature to include parenting practices and child development outcomes.

This model is supported by empirical literature demonstrating the mediating effects of activation levels^{53, 54}, interpersonal supports^{55, 56} and therapeutic alliance of BA and BA-based interventions on patient clinical outcomes of depressive and anxiety symptoms. Our own analyses of two recent parallel BA-based treatments demonstrated that both patient activation and interpersonal supports mediated the effects of one BA-based intervention on reduced maternal depressive symptoms⁵⁷. In addition, growing evidence suggests strong positive associations between maternal mental health and parenting practices^{58, 59}, including the provision of psychosocial stimulation⁶⁰ and breastfeeding^{61, 62}. We have also found that improved psychosocial stimulation mediated the effects of an integrated parenting and psychological treatment intervention on child mental development⁶³.

Analysis. We will extend our existing analysis plan to assess the proposed model quantitatively. Using Monte Carlo Methods for Assessing Mediation and structural equation modelling, we will estimate individual and multiple mediating pathways on patient and child outcomes. Unlike the majority of the prior literature, our analysis will follow key guidelines⁶⁴⁻⁶⁶ such as the assessment of multiple potential mediators, the use of a temporal design with hypothesized mediators being assessed at distinct time-points, a comparison of several active treatment groups with corresponding large sample sizes and adjusting for key variables at baseline (e.g., symptom severity).

3.4.9. Summary List of Potential Sensitivity Analyses

The trial has incorporated numerous sensitivity analyses to account for differences in participants' baseline characteristics, data collection time points and outcome variables such as depression and anxiety scores. Table 6 encompasses a few examples of the sensitivity analyses for this trial.

Table 6. Planned sensitivity analyses

Sensitivity Analysis	Purpose
Starting a new medication or change in medication between randomization and treatment initiation	To compare if the participants that started a new or changed medication were different from the larger sample
Accounting for the GAD-7 variable update from 'not at all sure' to 'not sure'	To determine whether participants that answered to GAD-7 with the 'not at all sure' option differed significantly from the larger sample
Inclusion of participants with SAE after randomization but before starting the treatment in the trial	To determine whether participants that had an SAE before treatment were different from the larger sample
Participants who were lost to follow up at randomization and did not start treatment but were asked to complete the follow up assessments	To include the lost to follow up after randomization before treatment data at 3,6 and 12 month follow up as part of intent-to-treat analysis
Considering number of days after baseline for completion of 3, 6 and 12 month data	To account for the time variability in completion of follow up data
Individuals who indicated yes to marijuana consumption but did not answer the follow up drug screening questions	To determine if participants who were using marijuana prior to updating the follow up marijuana screening question have significantly different outcomes than the remaining sample
Existing differences in Canada, Illinois and North Carolina jurisdiction in legalization of marijuana may impact individuals self-report of marijuana use at screening	To determine if there are differences between North Carolina and other sites in the outcome
Multiple imputation methods will be used to impute missing data and compare model results to the complete case analysis.	Should missing data lead to the use of multiple imputation methods, sensitivity analyses will compare the results of the models on the imputed data to the ones with the actual missing data included.

COVID-related Analyses:
 
The starting models to address COVID-related Aim 1 will compare mean baseline EPDS scores and mean GAD scores between the time periods (Phase 2 vs. Phase 3). The model to address COVID-related Aim 2 will include potential moderators. Using our originally-stated mean on the EPDS=7.93 (SD=4.68)³⁰, our power calculation indicates that a sample size of n=87 in each time period (N=174 across the entire period; or 184 including a 5% drop-out rate) is required to detect a clinically-meaningful difference of two or more points on the EPDS. This sample size will be used for the same number of participants enrolled during Phase 2 and Phase 3 of the trial (addressing Aim 1). To address COVID-related Aim 2, assuming a correlation of 0.1 between covariates, the sample size will be inflated to 204 (102 per time period).
 
To address COVID-related Aim 3, qualitative analyses using the same methods discussed in section 3.4.7 will be performed. Qualitative data will be analyzed to identify key themes related to barriers and facilitators using content analysis. Both barriers and facilitators will be categorized into internal, interpersonal and structural themes related to intervention delivery, impact and motivation, content and training and supervision.
	
COVID-related aim 1: Examining whether perinatal participants experience higher levels of depressive and anxiety symptoms during Phase 2 compared to those in Phase 3, whereby; 'Phase 2' is defined as period when IP allocation is treated as TM and 'Phase 3' is defined as the period when participants are randomized to IP and TM allocations by weighted randomization approach.
 
COVID-related aim 2: Examining potential moderators (e.g., treatment preference, trauma symptoms) of COVID-19 on treatment response among perinatal participants.
 
COVID-related aim 3: Exploring barriers and facilitators related to resuming IP treatment sessions from a multi-stakeholder perspective.

References

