3.4. Outcome analysis

3.4.1. Primary Analysis

All analyses will be run as both intent-to-treat (ITT, i.e., group that the participant was randomized to) and per protocol (i.e., group participant actually participated in*). SAS Version 9.4³⁵ or later will be used for all analyses. For non-inferiority analyses, a successful result will be based on the upper bound of the 95% confidence interval being less than or equal to the non-inferiority margin. Based on recent guidelines^{28, 29}, we will not adjust our two primary hypotheses for multiplicity as they do not involve different endpoints (i.e. both hypotheses test EPDS scores). For secondary superiority hypotheses, a two-sided significance level of $p<0.05$ will be used to denote statistical significance. Descriptive statistics will be calculated for all variables of interest. Continuous measures such as age and depressive symptoms will be summarized using means and standard deviations, whereas categorical measures will be summarized using counts and percentages.

*Note: The trial has n=21 protocol deviations. This number has been consistent since the last major COVID wave (March 2022).

Demographic (e.g., ethnicity, age, marital status) and other baseline variables (e.g., severity and chronicity) will be compared for potential differences between study groups (TM vs IP, and SP vs NSP) using two sample two sided t-tests for continuous variables (or Wilcoxon rank sum test in the case of non-normal data), and chi-square analyses for categorical variables (Fisher's exact tests in the case of low expected cell sizes). Those who withdrew from the trial will be compared to those who continued on baseline indices including maternal education and occupation.

The primary outcome of non-inferiority in EPDS scores will be compared between NSP vs. SP and TM vs. IP groups at 3-months using a t-test with a 10% and 13% margins of non-inferiority, respectively.

Primary Aim 1: Examine if a brief, BA psychological treatment delivered by non-specialist providers (NSP) is as effective in treating perinatal depressive symptoms as specialist-delivered treatment.

Aim 1 is to show that NSP is non-inferior to SP (N=479 per group, SPs vs NSPs, [Table 3](#)).

Primary Aim 2: Examine if a brief BA psychological treatment delivered through telemedicine (TM) is as effective in treating perinatal depressive symptoms as in-person treatment (IP).

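### SAP Table 6 sizes COVID-related Aim 2, a moderator question, at 204 women by adding about 11% to a main-effect sample size, which does not power an interaction

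*SAP*

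**What the plan says.** The COVID-related row of Table 6 (SAP section 3.4.9) gives one power calculation and then adapts it.

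- Inputs: "Using our originally-stated mean on the EPDS=7.93 (SD=4.68".
- Base size: "a sample size of n=87 in each time period (N=174 across the entire period; or 184 including a 5% drop-out rate". It "is required to detect a clinically-meaningful difference of two or more points on the EPDS". This is a comparison of Phase 2 with Phase 3, which is COVID-related Aim 1.
- Use of the base size: "This sample size will be used for the same number of participants enrolled during Phase 2 and Phase 3 of the trial". The parenthesis that follows ties this sentence to Aim 1.
- Aim 2 is described as: "Examining potential moderators (e.g., treatment preference, trauma symptoms) of COVID-19 on treatment response among perinatal participants".
- Size for Aim 2: "To address COVID-related Aim 2, assuming a correlation of 0.1 between covariates, the sample size will be inflated to 204 (102 per time period".

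For Aim 2 the table gives no interaction to be detected, no moderator distribution and no power. It does not say whether 204 is a minimum or a limit, or how 102 women per period would be chosen. Counts for Phases 2 and 3 are not reported; the only phase size given is 23 for Phase 1 (SAP section 3.4.1.1).

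**The concern.** A moderator of the period effect is tested by a difference between two period differences. With two equal periods and an evenly split moderator, that contrast has four times the variance of the period main effect. An allowance of about 11% for correlation among covariates does not cover this, because it addresses collinearity in a main-effect estimate.

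What is at stake is interpretation. A reader of Table 6 would take 204 as adequate for the moderator analysis and could read a null result as evidence that preference or trauma symptoms do not matter. At that size, a null result would say little about interactions near the only difference the table calls clinically meaningful, 2 points.

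**Working it through.** **Inputs.** From Table 6: SD 4.68, difference 2 points, 5% dropout, correlation 0.1. Two-sided alpha of 0.05 is the general rule for secondary superiority hypotheses in SAP section 3.4.1; Table 6 does not restate it. Power is not stated for this calculation. I assume 80%, which returns the table's own figure.

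**Reproducing the plan's figures.**

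1. Per period, normal approximation: 2 × (1.96 + 0.84)² × 4.68² / 2² ≈ 86. The t-test version gives 86.9, so 87 per period and 174 in total. A one-sided test (69 per period) or 90% power (117 per period) does not give 87.
2. Dropout: 174 / 0.95 = 183.2, so 184.
3. Aim 2: 184 / (1 − 0.1) = 204.4, so 204, or 102 per period. The increase is 204 / 184 − 1 = 10.9%.

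**Check of the inflation.** The factor for correlated covariates is 1 / (1 − R²). A correlation of 0.1 gives R² = 0.01, so 184 / 0.99 = 185.9, or 186. The 204 arises only if 0.1 is itself used as R². If the moderators were uncorrelated with one another, it would take ten of them, each correlated 0.1 with period, to reach R² = 0.1 (10 × 0.01).

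**Check of interaction power.** Assumptions, neither of them in the SAP: a binary moderator with share p, and an interaction of 2 points. Periods are equal, as in Table 6.

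- SE of the interaction = SD × √(1 / (N × 0.25 × p(1 − p))). With p = 0.5 this is SD × √(16 / N).
- At N = 204: 4.68 × √(16 / 204) = 1.31. The main-effect SE is 4.68 × √(4 / 204) = 0.66, half as large.
- Power = Φ(2 / 1.31 − 1.96) = 33%. For a 2-point main effect at the same N, power is 86%.
- Interaction detectable at 80% power: 2.80 × 1.31 = 3.7 points.
- After 5% loss (204 × 0.95 = 194): 32% power, 3.8 points.
- Evaluable women needed for a 2-point interaction at 80% power: about 688, or 725 with 5% dropout (688 / 0.95).

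**Sensitivity at N = 204.**

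| Moderator | Interaction | Power |
|---|---|---|
| 50/50 | 1 point | 12% |
| 50/50 | 2 points | 33% |
| 50/50 | 3 points | 63% |
| 50/50 | 4 points | 86% |
| 30/70 | 2 points | 29% |
| 20/80 | 2 points | 23% |
| Continuous | 1 point per SD | 33% |
| Continuous | 2 points per SD | 86% |

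With a 30/70 split the SE is 4.68 × √(1 / (204 × 0.25 × 0.21)) = 1.43, and the interaction detectable at 80% power is 2.80 × 1.43 = 4.0 points.

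**The case against.** The strongest reply is that the power figure depends on assumptions the SAP does not make. Its 2 points is a period difference, not an interaction. Power at 204 runs from 12% to 86% for interactions of 1 to 4 points. Trauma symptoms are measured by a continuous score (PCL-6). If treatment response means the PHQ-9 cut-off of less than 10 used elsewhere in both documents, the outcome is binary and an EPDS standard deviation does not apply. All of this stands, so the 33% must always carry its conditions. It does not rescue 204, which is computed from EPDS points for a period difference and has no stated link to any interaction, continuous or binary.

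It can also be said that the correlation slip makes the size larger (204, not 186) and so does no harm in itself. That is correct.

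Two stronger readings are tempting, and the documents do not support them.

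- *A reader might infer that Aim 2 is limited to 102 women per period, so that enrolled women are discarded.* The sentence about the size being used is tied to Aim 1, the 204 can equally be a minimum, and SAP section 3.4.1.1 plans the study analyses on the whole sample across phases. A limit is one possible reading of unclear text.
- *A reader might infer that each phase holds several hundred women, and compute the power gained by using them all.* Neither count is given. SAP section 1.4 reports 170 women who missed an item added on June 26, 2020. If they missed it because they had already enrolled, at least 170 − 23 = 147 were in Phase 2 by then, which exceeds 102. Phase 3 is less certain, because Table 6 confines it to the weighted-randomization period. Constant accrual (1,230 / 39 = 31.5 a month) over 4 to 5 months would give about 126 to 158. But accrual was evidently not constant: 30 women missed measures added on April 6, 2020, against 170 by June 26, so 140 were added in under three months. A full-sample power figure must wait for the actual counts.

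**Conclusion.** The point holds in this form. The 204 stated for COVID-related Aim 2 is a main-effect sample size enlarged by 10.9%, through a factor that treats a correlation as an R-squared, and it does not size a moderator analysis. If the interaction of interest is 2 EPDS points, with SD 4.68, two-sided 0.05, equal periods and an evenly split binary moderator, 204 women give about 33% power, and 80% power is reached only at about 3.7 points. An uneven binary split makes this worse; a larger true interaction makes it better. The interaction size and the moderator split are my assumptions.

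Whether the analysis is restricted to 102 per period is unclear, and that ambiguity should be removed. The consequence is limited: section 3.4.9 lists supporting analyses, and neither primary comparison depends on this figure.

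**What to change.** In Table 6, COVID-related Analyses:

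1. Remove 204 (102 per period) as the sample size for Aim 2, together with the correlation-based inflation.
2. State that all women enrolled in Phases 2 and 3, as Table 6 defines them, are analysed, and report both counts.
3. Specify the model: a period-by-moderator term, with delivery mode included because Phase 2 was telemedicine only (SAP section 1.5). Name the outcome, since treatment response could mean the EPDS score or the PHQ-9 cut-off.
4. State the interaction detectable at the actual phase counts, computed for the model as fitted.

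The cost is SAP wording and one recalculation; no new data are needed. The downside is that the stated detectable effect becomes less favourable than the 2 points a reader would now assume.
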